Table 1: Dose Titration Schedule

B.I.D Dose (mg)	Day 1-3	Day 4-7	Day 8-11	Day 12-14	Week 3-9	Week 10 5 day taper
8AM	0	0.5	1.0	1.0	1.5	1.0 - 1.0 - 0.5 - 0.5 - 0
8PM	0.5	1.0	1.0	1.5	1.5	1.5 - 1.0 - 1.0 - 0.5 - 0

Steady state period (wk 3-9 & medication taper (wk 10): Following titration, participants will continue taking medication as shown in Table 1 for seven weeks and with a 5-day taper in week 10 as used previously (Fox et al., 2012) and complete post treatment assessments. We have had no adverse events of medication

discontinuation using this taper schedule.

Discontinuation or dose adjustment due to side effects: While we anticipate subjects will tolerate study medication well, should participants experience side effects attributable to medication, titration will be stopped at the highest tolerable dose. Our previous studies indicated that 3mg/day was tolerable with adverse events rated as minimal or mild.

Medication compliance: Medication compliance will be assessed in multiple ways: 1) We will include 2X/daily cell/home phone prompts as a reminder to take study medication. This strategy has been successfully implemented in previous addiction trials (Kranzler et al., 2004); (Simpson et al., 2005). If a subject does not have a phone, a prepaid phone will be provided for the duration of the trial. 2) A riboflavin marker will be included in study medication and urines will be assessed by fluorescence at each study visit and quantitatively measured every other week. 3) We will assess GUA levels as in our previous study at week 3, 6 and 9. Importantly, we will explore the relationship between compliance and cocaine use outcomes.

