Neutral Imagery Condition (Condition 2)	
3:40 PM	Schedule as in condition 1
Stress / Drug Cues (Condition 3)	
4:20 PM	Schedule as in condition 1

Order of imagery conditions is counterbalanced across subjects.

Study Assessments: Assessments include the following:

- 1) Sample description and eligibility including sociodemographics; psychosocial, substance use, and medical history; psychiatric assessment using the:
 - i) Structured Clinical Interview of Diagnostics (SCID-I) for DSM-V,(First et al., 1995),
 - ii) Connors ADHD Assessment and Rating Scale (CAARS,(Conners, 1999)
 - iii) vitals
 - iv) CBC, blood chemistry
 - v) urinalysis
 - v) pregnancy testing;
- 2) Primary SUD outcomes assessed using the:
 - i) Substance Use Calendar (SUC) developed by Miller and Del Boca (Miller and Del Boca, 1994) and based on the Time-Line Follow-Back (Sobell and Sobell, 1992; Sobell et al., 1996) and urinalysis for objective drug use assessed 2X/weekly during the 10 week period (20 urines);
- 3) Secondary Outcome Measures assessing drug craving using the standard brief versions of the Drug Craving questionnaires for cocaine (Cocaine Craving Questionnaire: CCQ,(Tiffany et al., 1993), cannabis (Marijuana Craving Questionnaire: MCQ, (Heishman et al., 2009)), alcohol (Alcohol Urges Questionnaire: AUQ, (Bohn et al., 1995) and nicotine (Questionnaire of Smoking Urges: QSU(Tiffany et al., 1993); (Tiffany and Drobes, 1991). Drug abstinence symptoms using standardized cocaine selective severity assessment (CSSA, (Kampman et al., 1998), Clinical Alcohol Withdrawal Assessment-Revised (Sullivan et al., 1989); The Cannabis Withdrawal Scale (Allsop et al., 2011); and the Minnesota Nicotine Withdrawal Scale (MNWS; (Hughes et al., 1986). Other drug use and drug related problems will be measured using the SUC; urinalysis; breathalyzer; the Addiction

Severity Index (ASI; (McLellan et al., 1992)) and Treatment Services Review (McLellan et al., 1992); stress (Perceived Stress Scale; (Cohen et al., 1983)); anxiety (Hamilton Anxiety Rating Scale, Ham-A; (Hamilton, 1960)) and depressive symptoms (Hamilton Depression Rating Scale, Ham-D, (Hamilton, 1960)). cognitive flexibility will be assessed using the Stroop Color Word Test; (Golden, 1975),

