4) Safety and Compliance Assessment using vital signs; the Systematic Assessment for Treatment Emergent Effects (SAFTEE; (Rabkin et al., 1992)) to assess adverse events; and medication compliance assessed using pills counts, riboflavin markers and plasma levels of GUA. Each of these instruments are widely used, state-of-the-art and have strong psychometric properties.

5) Predictor variables:

The Childhood Trauma Questionnaire (CTQ) (Bernstein, 1998) is a 28-item self-report inventory that provides a brief screening for histories of abuse and neglect. The CTQ will be administered at intake.

The Chronic Stress Checklist (CSC) adapted from the Cumulative Adversity Interview (Turner and Wheaton, 1995) will be administered at intake.

The Perceived Stress Scale (PSS) (Cohen, Kamarck, & Mermelstein, 1983) is a 14 item self-report assessing the degree to which situations are appraised as threatening or demanding. The PSS will be administered at intake and weekly.

The Emotion Regulation Scale (ERS) (DERS) (Nock et al., 2008) is a 36-item questionnaire to provide a comprehensive measure of the difficulties in emotion regulation. The ERS (DERS) will be administered at intake and weekly.

6) Cognitive Control Testing for Executive Function:

The Shipley Institute of Living Scale (SHIPLEY) (Shipley, 1940) has been widely used to assess cognitive functioning and impairment. The Shipley will be administered at the intake.

CANTAB (Cambridge Cognition, Inc) Battery will be administered during intake appointments and includes cognitive tests of executive function.

7) Laboratory Challenge Assessments:

Craving: Participants will rate the intensity of their desire to use primary and secondary drug of choice at the current time using a 10-point visual analog scale (0= "not at all" and 10= "extremely high"). Visual analog scales will also be administered for cocaine, cannabis, alcohol and nicotine craving.

Anxiety: Participants will rate how "*anxious, nervous and jittery*" they feel at the current time using a 10-point visual analog scale anchored as above. *Mood:* Differential Emotion Scale (DES: (Izard, 1972)): comprises 30 emotional words. Participants rate on a 5-point scale the extent to which each word describes current feelings.

Cardiovascular: An ambulatory ECG (Holter) GE Seer and Seer Lite recorders (digital sampling 125 sps) will be used to measure HRV, and recordings will be scanned using a GE Mars Ambulatory ECG system (PC, version 7).

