versus placebo, we found it to be safe and well tolerated. In the initial study (Fox et al., 2012), the most common side effects were mild tiredness and fatigue (guanfacine 24%; placebo: 8%) and headaches (guanfacine 18%; placebo 8%). All symptoms dissipated over time without further intervention. Side effects from a dose-ranging study comparing placebo, 2 and 3 mg/day of guanfacine (Fox et al., 2009) indicated mild symptoms which dissipated rapidly without intervention in 7/21 individuals in the placebo group (33.33%), 5/12 individuals in the guanfacine (2mg) group (41.7%) and 4/11 individuals in the guanfacine (3mg) group (36.4%). Furthermore, there were no significant blood pressure differences across medication and placebo groups. Also, there were no significant sex differences in reported side effects. There is no evidence that guanfacine will pose a greater risk in the proposed study sample than those previously reported. Importantly, patients will be seen in person on a weekly basis when information on any potential side effects will be collected; in case of any concerns, the study physician will be alerted immediately.

2) Risk of including subjects who are otherwise inappropriate

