- Where appropriate, how will pertinent information be returned to, or shared with subjects at a later date? *Write here*

SECTION IV: PROTECTION OF RESEARCH SUBJECTS**Confidentiality & Security of Data:**

1. What protected health information (medical information along with the HIPAA identifiers) about subjects will be collected and used for the research?

Results of the physical examination, psychological assessments, self-reports, and data collected during the lab sessions will be collected and used for research. The proposed study will be conducted by specialized and trained research staff using standardized biophysiological and psychosocial assessments. Data collected and analyzed in the study will be derived from three main sources (1) semi-structured clinical interviews and self-rating scales: psychiatric history, medical history, levels of alcohol and substance use and demographic self-reports of age, race, socioeconomic status, marital status, educational and occupational levels. (2) Biophysiological data: includes heart rate, blood pressure, saliva and plasma HPA axis markers (cortisol and ACTH). Additionally, health checks prior to enrollment will comprise a physical examination and blood work. (3) Urine and breathalyzer data: will be used to confirm alcohol and substance use. It will be collected at intake and during weekly appointments.

2. How will the research data be collected, recorded and stored?

Research data will be collected on paper assessments and using Yale University's REDCap system. All research data is stored in two places--one as a hardcopy in a locked file, with records identified only by the participant's study number, and the second in computerized databases protected by two-level password systems on Yale encrypted desktop computers.

3. How will the digital data be stored? CD DVD Flash Drive Portable Hard Drive Secured Server Laptop Computer Desktop Computer Other

4. What methods and procedures will be used to safeguard the confidentiality and security of the identifiable study data and the storage media indicated above during and after the subject's participation in the study?

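### Side-effect collection is stated as weekly while the dose rises on days 4, 8, 12 and 15; using both existing twice-weekly visits in titration would be a cheap improvement

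*Combined protocol and SAP*

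**What the plan says.** Table 1 (Section I, item 4) divides titration into "Day 1-3 Day 4-7 Day 8-11 Day 12-14", with the full dose from week 3. The paragraph on discontinuation and dose adjustment gives the tolerability rule: "should participants experience side effects attributable to medication, titration will be stopped at the highest tolerable dose".

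The only stated frequency for asking about tolerability is in Section I, item 11, under the risk of the study drug: "patients will be seen in person on a weekly basis when information on any potential side effects will be collected". The same sentence says that the study physician is told at once of any concern. The behavioral-support paragraph also includes safety checking in medication management, which is delivered with the weekly therapy session. The list of study assessments names the instruments, "Safety and Compliance Assessment using vital signs; the Systematic Assessment for Treatment Emergent Effects", but gives no days for them.

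Visits are more frequent than that. The primary outcome uses "urinalysis for objective drug use assessed 2X/weekly during the 10 week period (20 urines", and contingency management rewards attendance twice a week. No section ties side-effect or blood-pressure checks to both visits, and none requires a check before a dose increase. The other vital-sign and heart-rate recordings fall at intake and in the laboratory sessions (before medication and in week 8-9), outside titration.

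**The concern.** A rule that stops escalation at the highest tolerable dose works best if tolerability at one level is known before the next level starts. With four increases in two weeks and one stated check per week, some increases come before anyone is scheduled to ask. For example, a woman checked on day 3 at 0.5 mg/day would next be checked on day 10 at 2.0 mg/day, after two increases.

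The effects of interest include hypotension and bradycardia, which item 11 names and which are found better by measurement than by waiting for a complaint. The background in Section II reports lower basal heart rate (p = .001) and blood pressure (systolic p < .02, diastolic p = .01) than placebo at 2 mg/day, a level reached here on day 8. It also reports that basal heart rate fell more in females. No magnitudes or symptomatic events are given. At stake is the timeliness of dose adjustment for the 50 women planned for guanfacine. The primary analysis is not affected.

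**Working it through.** **Inputs.** Dose periods and doses come from Table 1, and the two-week titration length from the Research Plan. The weekly frequency comes from item 11, and twice-weekly attendance from the assessment list and the contingency-management paragraph.

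**Step 1: dose levels.** Daily total = 8AM dose + 8PM dose.

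| Level | Days | Sum (mg) | Total (mg/day) | Next increase |
|---|---|---|---|---|
| L1 | 1-3 | 0 + 0.5 | 0.5 | day 4 |
| L2 | 4-7 | 0.5 + 1.0 | 1.5 | day 8 |
| L3 | 8-11 | 1.0 + 1.0 | 2.0 | day 12 |
| L4 | 12-14 | 1.0 + 1.5 | 2.5 | day 15 |
| Target | from 15 | 1.5 + 1.5 | 3.0 | none |

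This reproduces the plan's 3 mg/day after two weeks. Section II describes the proposed titration as 16 days. The count here uses Table 1, which is explicit.

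**Step 2: weekly checks, by calendar day.** L1 and L2 lie wholly in week 1, and L3 and L4 wholly in week 2. One visit per week therefore meets one level in each week: 1 + 1 = 2 checked and 4 - 2 = 2 not checked. With visits 7 days apart:

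- days (1,8), (2,9) or (3,10): L1 and L3 checked; the increases on days 8 and 15 are not preceded by a check at that dose
- days (4,11): L2 and L3 checked; days 4 and 15 are not
- days (5,12), (6,13) or (7,14): L2 and L4 checked; days 4 and 12 are not

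**Step 3: weekly checks, by dosing hour.** Assume visits fall between 8AM and 8PM. The day 1 capsule with active dose is at 8PM, so L1 can be observed on days 2-3. The day 12 rise is in the 8PM dose, so L3 runs through the day 12 visit and L4 is days 13-14. Six placements still check 2 of 4, and (1,8) checks only L3, which is 1 of 4. The number not checked is never below two.

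**Step 4: checks at both weekly visits.** Assume visits on days a, b, a+7 and b+7, with b - a equal to 3 or 4. That gives seven placements.

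| (a,b) | Levels missed, calendar day | Levels missed, dosing hour |
|---|---|---|
| (1,4) | 1 | 2 |
| (1,5) | 0 | 2 |
| (2,5) | 0 | 1 |
| (2,6) | 0 | 0 |
| (3,6) | 0 | 0 |
| (3,7) | 0 | 0 |
| (4,7) | 1 | 1 |
| Mean | 2/7 = 0.29 | 6/7 = 0.86 |

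The means treat the seven placements as equally likely. All four levels are checked in 5 of 7 placements by calendar day and in 3 of 7 by dosing hour. The longest gap between checks is 4 days, against 7 with weekly checks.

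**Step 5: an aligned example.** Visits on days 3, 7, 10 and 14 fall in L1, L2, L3 and L4 on either count.

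**The case against.** The strongest reply is that the word weekly in item 11 stands in a risk narrative, not in a schedule of assessments, and that the protocol uses the word loosely. Section IV says of urine and breath data that "It will be collected at intake and during weekly appointments", whereas the assessment list sets urine testing at twice a week. If staff already ask about side effects at both visits, most of the gap closes (step 4). This stands as a real uncertainty. It does not remove the point, because weekly is still the only frequency stated for side effects and two sites have to follow the same text.

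The documents also give several reasons for low risk, and these stand:

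- Earlier use of the titration is described as safe with mild effects. Item 11 reports no significant blood pressure differences between groups and no sex differences in side effects.
- A randomized 8-week outpatient pilot at 3 mg/day, described as using the same titration, was acceptable to patients with high compliance. It is weak evidence: 7 people took guanfacine, 2 of them women, and its check schedule is not given.
- Women with sitting pressure below 100/50 or important EKG conduction findings are excluded.
- The physician is alerted at once to concerns, and a medical monitor oversees adverse events at both sites. Both act on problems once found; neither schedules a check.

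There is other frequent contact: "2X/daily cell/home phone prompts as a reminder to take study medication" and daily app surveys. Neither is stated to ask about side effects.

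Finally, nothing in the documents requires a check at every level before the next. That is correct: this is an improvement to the plan, and the plan breaks no rule of its own.

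**Conclusion.** As written, at least two of the four increases have no scheduled tolerability check at the preceding dose. At those steps the stop rule relies on what a woman volunteers, or acts at the next visit, at most a week later. The count rests on Table 1 and on taking weekly at its word. If side effects are in fact collected at both visits, the shortfall is 0.29 to 0.86 of four levels on average, under the placement assumptions in step 4.

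A reader might infer that women are escalated without monitoring, or that a safety failure has been shown. The documents do not support that. Women are seen twice a week, the stop rule still operates, the safeguards listed above apply, and the experience reported is reassuring. The documents give no rate of unreported intolerance, so harm cannot be quantified, and it is probably modest. This is a cheap improvement of minor severity.

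**What to change.** For weeks 1-2, amend item 11 to state that side effects (SAFTEE or a brief version), seated blood pressure and heart rate are collected at both existing twice-weekly visits, and give the same timing in the assessment list. Where practicable, set the start day so that a visit falls within each dose level, for example days 3, 7, 10 and 14, provided that this does not prolong the 3-day abstinence period.

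Where a level has no visit, a brief phone symptom check before the increase is optional. It is feasible because the plan already says: "If a subject does not have a phone, a prepaid phone will be provided for the duration of the trial". It would give symptoms but no blood pressure or heart rate.

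The cost is protocol wording plus two more brief checks per woman, or 2 x 100 = 200 over the trial (about 17 to 33 staff hours at an assumed 5 to 10 minutes each). No visits are added. Without alignment, some placements still miss one or two levels.

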positive effects in women but not in men (Fox et al., 2012; [name] et al., 2011). Preliminary data also showed that GUA 3 mg/day (bid dosing) vs. placebo led to higher cocaine-negative urines in an 8-week outpatient setting only in women and not men.

4. **Research Plan:** Summarize the study design and research procedures using non-technical language that can be readily understood by someone outside the discipline. **Be sure to distinguish between standard of care vs. research procedures when applicable, and include any flowcharts of visits specifying their individual times and lengths.** Describe the setting in which the research will take place.

The current study will test **GUA (3 mg/day) vs Placebo (PBO)** in a 10-week clinical trial across 2 sites in a total of 100 SUD women.

All participants will be titrated to steady-state medication levels over 2 weeks followed by a **7-week treatment period using a standard cognitive behavioral relapse prevention** with medication management and contingency management (CM) for treatment attendance. A 5-day taper will be implemented in week 10. All participants will also take part in **two laboratory challenge test sessions**: one at pre-treatment (pre-tx) and one during week 9 of treatment, to assess provoked drug craving and cognitive flexibility under stress, drug cue and neutral cue conditions in a randomized and counterbalanced order.

Pre-treatment Intake Procedures: Following the initial telephone screening, eligible participants will meet with the research staff to obtain written informed consent. Subjects will complete 2-3 intake appointments, and during these appointments they will be consented, screened of substance use, and provide demographic and psychiatric data. Physical examinations, blood work, a urine test, and a breathalyzer test will also be completed. All subjects will meet with the study physician, and if deemed eligible, after discussion of risk and benefits, subjects will be randomized into the study.

Randomization: Eligible subjects will then be randomized in a double blind manner to either placebo or 3 mg/day (bid dosing) of GUA balancing the patients on age, education, race, ADHD and severity of drug use.

Medication Titration Period (wk 1-3): Following a 3-day abstinence period, a 2-week titration period, previously found to be safe and with only mild adverse effects (Fox et al., 2014; Fox et al., 2012; Milivojevic et al., 2017) will be initiated (see Table 1).

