Laboratory Challenge Component: An identical laboratory challenge session will be conducted in the initial week of outpatient treatment Week 0, prior to medication, and again in Week 9. Our standard imagery script development procedures will be used to develop the stress, drug cue and neutral relaxing imagery scripts. The stress imagery script will be based on participants' description of a recent personal event experienced as "most stressful", and determined as such by rating it above 8 on a 10-point stress scale. These may include breakup with a significant other, marital conflict or job-related stress. A drug cue script will be developed based on situations involving people places and things pertaining to drug use that led to wanting drug and eventual drug use (e.g., meeting drug using friend, going by a favorite bar, etc). The neutral script will be developed from a personal non-alcohol-related relaxing situation. A 5-minute 'script' of each scenario will be written using Scene Construction Questionnaires ([name], 2009) where verbal and non-verbal responses, and physiological and bodily sensations regarding the events will be obtained. A script is then written following standard format and content procedures and scripts are then recorded onto audiotape for guided imagery in the laboratory sessions ([name], 2009). On the morning of the day prior to the initial laboratory session, participants will be brought into the testing room to receive training in relaxation and imagery procedures, as well as familiarize themselves with the subjective rating forms. The 10-min relaxation training will comprise muscle relaxation procedures in order to help subjects reach a relaxed state prior to imagery exposure during the laboratory sessions.

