9. How will **eligibility** be determined, and by whom? Write here

Research staff will determine eligibility. Potential subjects will complete an initial telephone screening, and then be scheduled to meet with research staff to complete a brief screening. The screening will include questions on substance use, psychiatric history, an EKG, blood work and a urine test. Subjects will meet with the study physician for a physical examination.

10. **Risks:** Describe the reasonably foreseeable risks, including risks to subject privacy, discomforts, or inconveniences associated with subjects participating in the research.

- 1) Risk associated with taking the study drug, Guanfacine
- 2) Risk of including subjects who are otherwise inappropriate
- 3) The imagery procedure
- 4) Increased risk for relapse
- 5) Increased risk to subject privacy

11. **Minimizing Risks:** Describe the manner in which the above-mentioned risks will be minimized.

1) Risk associated with taking the study drug, Guanfacine

Previous research established use of GUA in children with ADHD and tic disorders have used doses ranging from 1.5 to 4 mg/day (Hunt et al., 1995); (Scahill et al., 2001). Side effects that have occurred in clinical trials in adults with guanfacine include dry mouth, sedation, weakness, dizziness, impotence, and constipation. Hypotension and bradycardia may also occur. In the previous work with 3-week treatment of GUA (3mgs/day)

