The screening of subjects using the inclusion and exclusion criteria, and the comprehensive medical and psychiatric evaluation will minimize the risk of including subjects who are otherwise inappropriate. All subjects recruited will receive a comprehensive physical examination and laboratory blood work to ensure good physical health status. The physical examinations will be conducted by the study medical personnel, who will be aware of study entry criteria and will manage recruitment as well as physical and medical assessment for this study. Routine laboratory blood work (CBC, electrolytes, etc.) and blood samples for medication levels will be collected. Abnormal findings pertaining to physical health and blood chemistry will be evaluated further by the study physician and appropriate medical advice will be provided. These are routine medical procedures and should add no risks other than those normally associated with these procedures. However, the research staff, with advice from the study physician, will ensure that potential participants who may be excluded from research due to medical reasons or pregnancy, or who are in immediate need for medical or psychiatric attention, will be referred to primary care/psychiatric care facilities so they can receive the appropriate clinical care needed to address their condition. Breath screening and urine collections are performed primarily as safeguards to contamination of data and should add no risks other than those normally associated with these procedures. Pregnant women will be excluded from the study. Female subjects will be asked questions to assess the possibility of pregnancy, and if this information fails to establish that pregnancy is highly unlikely then a serum beta HCG pregnancy test will be done prior to participation.

3) The imagery procedure

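### The entry pregnancy test depends on self-report, and no visible text schedules a test or gives a study-drug rule for pregnancy during 67 dosing days

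*Combined protocol and SAP*

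**What the plan says.** Text on pregnancy at entry appears in several places in the combined protocol:

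- **Section I, item 11 (Minimizing Risks), part 2.** Women are asked about possible pregnancy; then "if this information fails to establish that pregnancy is highly unlikely then a serum beta HCG pregnancy test will be done prior to participation". The test is tied to participation, not to the first dose.
- **Section I, item 4 (Research Plan), Study Assessments, list 1.** "pregnancy testing" is one entry among the description and eligibility assessments. No condition, sample type or timing is given.
- **Section I, item 9 (eligibility).** "The screening will include questions on substance use, psychiatric history, an EKG, blood work and a urine test".
- **Section I, item 4, Pre-treatment Intake Procedures.** "Physical examinations, blood work, a urine test, and a breathalyzer test will also be completed". Like item 9, this does not name a pregnancy test.
- **Section I, item 8, exclusion viii.** Pregnancy, nursing and refusal of reliable contraception all exclude.

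For the dosing period:

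- Item 4 says that "participants will continue taking medication as shown in Table 1 for seven weeks and with a 5-day taper in week 10".
- The discontinuation and dose-adjustment paragraph deals with side effects: "should participants experience side effects attributable to medication, titration will be stopped at the highest tolerable dose".
- The on-study safety assessments (Study Assessments, list 4) are vital signs, the SAFTEE and compliance measures.
- The referral in item 11, part 2 is for "potential participants who may be excluded from research due to medical reasons or pregnancy", that is, before entry.
- The safety monitoring plan (item 12) counts a birth defect as a serious adverse event. It does not say how a pregnancy on study would be found or handled.

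**The concern.** An exclusion is only as good as the procedure that applies it. Here the only stated procedure relies on self-report, with an assay as back-up when the answers do not reassure. Elsewhere the same protocol does not settle for self-report: entry requires a positive urine toxicology screen, drug use is checked by urinalysis, and compliance is checked by riboflavin marker and plasma level.

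Two things are at stake. First, a woman who is pregnant without knowing it can meet every written step and start drug. Second, a pregnancy that begins during dosing has no scheduled test to detect it, and once it is found staff have no written instruction on study drug. Weekly review asks about side effects, so an early pregnancy without symptoms could go unnoticed while dosing continues.

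The protocol itself says that it does not regard the risk of taking guanfacine as minimal (item 12), although it also says that the studies are not high risk.

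**Working it through.** **1. Entry rule: the sections side by side.**

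| Section | Is every woman tested before the first dose? |
|---|---|
| Item 11, part 2 | No; only if the answers leave pregnancy plausible |
| Item 4, Study Assessments, list 1 | Not stated; pregnancy testing is listed with no condition |
| Item 4, intake paragraph | Not stated; blood work and a urine test, purpose not given |
| Item 9, eligibility | Not stated; blood work and a urine test, purpose not given |

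If the list entry is read as shorthand for item 11, the conditional rule governs and a woman with reassuring answers is not tested. If the list entry is read as universal testing, the sentence in item 11 is wrong. On either reading the item 11 sentence needs to change.

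**2. Length of the trial.** Two weeks of titration + 7 weeks at steady state + week 10 for the taper = 10 weeks, which reproduces the stated length.

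**3. Dosing days, from Table 1** (daily dose = 8 AM dose + 8 PM dose).

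| Period | Days with a dose | Daily dose (mg) | Total (mg) |
|---|---|---|---|
| Day 1-3 | 3 | 0 + 0.5 = 0.5 | 1.5 |
| Day 4-7 | 4 | 0.5 + 1.0 = 1.5 | 6 |
| Day 8-11 | 4 | 1.0 + 1.0 = 2.0 | 8 |
| Day 12-14 | 3 | 1.0 + 1.5 = 2.5 | 7.5 |
| Week 3-9 | 49 | 1.5 + 1.5 = 3.0 | 147 |
| Taper | 4 | 2.5, 2.0, 1.5, 1.0 | 7 |
| **Sum** | **67** | | **177** |

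The fifth taper day is 0 mg at both times, so the table spans 68 days but has 67 with drug. The background text in Section II mentions a 16-day titration; on that figure the count would be 16 + 49 + 4 = 69.

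**4. Scheduled pregnancy tests in those days:** none found, although 20 urines are planned for drug testing (2 per week × 10 weeks).

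**5. What periodic tests would change.** Week 4 is days 22-28 and week 8 is days 50-56. Counting from the first dose, with a test just before it:

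- Tests on days 28 and 56: intervals of 28, 28 and 11 days.
- Tests on days 22 and 50: intervals of 22, 28 and 17 days.
- Widest spacing, days 22 and 56: intervals of 22, 34 and 11 days.

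The longest run of dosing days without a test falls from 67 to 28, or to 34 at worst. The 67 is also counted from the first dose. Where no entry test was done, the time since any test is longer still.

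**The case against.** The strongest objection is that nothing here contradicts anything else. The assessment list gives bare names, with no method or timing for this item, and item 11 supplies the method. The intake and eligibility paragraphs are short summaries that neither name nor rule out a pregnancy test. This stands. A reader might infer that the protocol gives two conflicting rules, or that the two sites will test differently. The documents do not establish either: there is one medical monitor for both sites (item 12), and the sites hold joint weekly meetings (item 13). The defect is the content of the conditional rule.

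Second, safeguards exist. The contraception criterion looks ahead to the dosing period. Weekly sessions combine therapy with medication management by medical practitioners, including safety checks. Adverse events go to a medical monitor. So a detected pregnancy would reach someone able to decide. This stands too, but none of these measures tests for pregnancy or states the decision on study drug.

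Third, the file is incomplete. Consent pages were removed, and the paragraph on behavioral support breaks off in mid-sentence. The statement that no rule exists is therefore limited to the visible text.

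Fourth, no harm is quantified. The documents give no fetal-risk information for guanfacine and no pregnancy rate, and only the guanfacine arm (50 of 100) would be exposed to drug. The interval between on-treatment tests is a matter of choice. The point also leaves power and the primary analysis untouched. All of this is right, and it makes the argument one of precaution.

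**Conclusion.** The concern holds in a limited form. As written, item 11 lets a woman with reassuring answers be randomized and dosed with no pregnancy test, although pregnancy is an exclusion and every participant is a woman aged 18-55. The visible text then schedules no pregnancy test over 67 dosing days (177 mg on the full guanfacine schedule; 69 days if titration takes 16 days). It also gives no rule for study drug if pregnancy occurs. This is more than missing detail, because following the stated rule gives a weaker safeguard than testing everyone on samples already being taken.

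A reader might go further and infer that guanfacine is a known fetal hazard, or that some number of women would be affected. The documents support neither, and no such number is estimated here.

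The verdict assumes that Table 1 is the operative dose schedule and that the missing consent pages do not already set a test schedule and stopping rule. Even if they do, staff at both sites need those rules in the protocol body. The change should be made, but it does not threaten the trial's conclusions.

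**What to change.** **Item 11, part 2.** Replace the conditional sentence with wording such as:

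> Every woman of childbearing potential must have a negative HCG test (serum or urine, on a sample already collected at intake) before randomization, and a negative urine test at the Week 0 laboratory session before the first dose. Questions are used only to document that a woman is not of childbearing potential.

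Define childbearing potential in the same place. The Week 0 session suits the repeat test: "An identical laboratory challenge session will be conducted in the initial week of outpatient treatment Week 0, prior to medication", and Table 2 already has a urine check on arrival.

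**Item 4, Study Assessments, list 1.** State who is tested and when, to match.

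**Item 4, discontinuation paragraph.** Add:

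- A woman who tests positive before the first dose is not dosed.
- A pregnancy found during dosing stops study drug, with any taper decided by the study physician. She is referred for care and the event is reported to the medical monitor.
- In either case, a woman already randomized stays in the analysis as randomized.

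**Optional.** Urine pregnancy tests on urine already collected, for example in weeks 4 and 8. The interval is a choice, not a figure from the documents.

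**Cost.** A protocol amendment at both sites, with matching consent wording if needed. For 100 randomized women the required part is at most about 100 intake assays + 100 Week 0 urine tests = 200, plus some intake assays for women who later fail screening. Tests in weeks 4 and 8 add up to 2 × 100 = 200, for about 400 in all. The samples and visits are already planned, so no added visit should be needed. The documents give no assay price; that these tests are inexpensive is an assumption.
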